16.1. Study Information

16.1.1. Protocol and Amendments

Protocol

An Open-Label, 3-Period, Fixed Sequence Study to Evaluate the Effect of an H2 Antagonist and a Proton Pump Inhibitor on the Single Dose Pharmacokinetics of LOXO-292 in Healthy Adult Subjects

Protocol Status: Final

Original Final Protocol Date: 20 June 2019

Protocol Version: 1

Investigational Product: LOXO-292

Protocol Reference Number: LOXO-RET-19075

Covance Study Number: 8412-056

IND Number: 133193

for

Loxo Oncology, Inc.

A wholly owned subsidiary of Eli Lilly and Company
[name]
[name]

by

Covance Early Clinical Services
[name]
[name]

Information described herein is confidential and may be disclosed only with the express written permission of the Sponsor.

STUDY IDENTIFICATION

Sponsor	Loxo Oncology, Inc. [name] [name] [contact] (Main Telephone No.)
Sponsor's Study Contact	PPD
Sponsor's Medical Contact	PPD
Bioanalytical Laboratory	PPD
Protocol Medical Writer	PPD

PRINCIPAL INVESTIGATOR AND SPONSOR – SIGNATORIES

**An Open-Label, 3-Period, Fixed Sequence Study to Evaluate the Effect of an
H2 Antagonist and a Proton Pump Inhibitor on the Single Dose
Pharmacokinetics of LOXO-292 in Healthy Adult Subjects**

SPONSOR: Loxo Oncology, Inc.
[name]
[name], USA

**SPONSOR'S
REPRESENTATIVE:**

PPD

PPD

PPD

PPD

SYNOPSIS

Title of study: An Open-Label, 3-Period, Fixed Sequence Study to Evaluate the Effect of an H2 Antagonist and a Proton Pump Inhibitor on the Single Dose Pharmacokinetics of LOXO-292 in Healthy Adult Subjects

Objectives:

The objectives of this study are:

Primary:

- To assess the effect of multiple doses of an H2 antagonist (ranitidine) administered with a single dose of LOXO-292 on the pharmacokinetics (PK) of LOXO-292 under fasted conditions in healthy adult subjects.
- To assess the effect of multiple doses of a proton pump inhibitor (PPI) (omeprazole) administered with a single dose of LOXO-292 on the PK of LOXO-292 given with a low-fat meal in healthy adult subjects.

Secondary:

- To determine the safety and tolerability of a single dose of LOXO-292 under fasted conditions alone, in combination with an H2 antagonist (ranitidine) under fasted conditions, and in combination with a PPI (omeprazole) given with a low-fat meal in healthy adult subjects.

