Twenty healthy, adult, male and female subjects (women of nonchildbearing potential only) are considered sufficient to assess the effect of multiple doses of an H2 antagonist (under fasted conditions) or a PPI (given with a low-fat meal) on the PK of LOXO-292.

Every attempt will be made to enroll at least 3 subjects of each sex in the study.

Subjects who withdraw or drop out of the study may be replaced if deemed necessary by the Sponsor.

Diagnosis and main criteria for inclusion:

Male subjects and female subjects of nonchildbearing potential, between 18 and 55 years of age, inclusive, at Screening, and within body mass index (BMI) range 18.5 to 32.0 kg/m², inclusive. Subjects will be in good general health, based on medical history, PE findings, vital signs, ECG, and clinical laboratory tests at Screening and Check-in (Day -1), as determined by the Investigator (or designee).

Investigational products, dose, and mode of administration:

LOXO-292 will be supplied by Loxo Oncology as 80 mg capsules for oral administration. Ranitidine will be supplied by Covance as 150 mg tablets for oral administration. Omeprazole will be supplied by Covance as 40 mg capsules for oral administration

Period 1: Subjects will be administered 160 mg LOXO-292 (2 x 80 mg capsules) on Day 1 administered under fasted conditions.

Period 2: Subjects will be administered 150 mg of rantidine twice daily from Day 8 of through Day 18, inclusive, administered with 160 mg LOXO-292 on Day 12 under fasted conditions.

Period 3: Subjects will be administered 40 mg of omeprazole once daily from Day 19 through Day 29, inclusive, administered with 160 mg LOXO-292 on Day 23 with a low-fat meal.

Duration of subject participation in the study:

Planned Enrollment/Screening Duration: up to 28 days (Day -29 to Day -2).

Length of Confinement: a total of 31 days (30 nights), from the time of Check-in (Day -1) through the 168-hour PK blood draw and end of study assessments (Day 30).

Follow-up Phone Call: 7 days (\pm 2 days) after EOT or ET.

Planned Study Conduct Duration: approximately 60 days

Criteria for evaluation:

Pharmacokinetics:

Serial PK blood samples for the analysis of plasma LOXO-292 concentrations will be collected from predose through 168 hours postdose.

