25. Significant history or clinical manifestation of any metabolic, allergic, dermatological, hepatic, biliary, renal, hematological, pulmonary, cardiovascular (including any prior history of cardiomyopathy or cardiac failure), gastrointestinal, neurological, or psychiatric disorder (as determined by the Investigator), or cancer within the past 5 years (except localized basal cell, squamous, or in situ cancer of the skin)
26. History of diabetes mellitus; hemoglobin A1c $\geq 6.5\%$
27. History of congenital nonhemolytic hyperbilirubinemia (eg, Gilbert's syndrome)

28. Have previously completed or withdrawn from any other study investigating LOXO-292, and have previously received the investigational product
29. Has been on a diet incompatible with the on-study diet, in the opinion of the Investigator (or designee), and as confirmed by the Sponsor, within the 30 days prior to the first dosing and through EOT or ET
30. Subjects who, in the opinion of the Investigator (or designee), should not participate in this study

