All study drugs will be administered orally with approximately 240 mL of water. An additional 100 mL of water may be administered if needed.

Each unit dose will be prepared by qualified clinical staff. Each unit dose container will be appropriately labeled.

Appropriate unit dose(s), as described above, will be administered to consecutively numbered subjects. Although the timing of events requires that each subject will be consistently administered the appropriate dose at a specific time, the exact dose time of consecutive subjects may be staggered to obviate the need to have all subjects on precisely the same study schedule.

For each dose, the subject's actual dose time will be recorded in the source documents and transcribed into the eCRF.

Subjects will be instructed not to crush, split, or chew the study drugs.

Subjects will not lay supine for 4 hours following LOXO-292 dose administration, except as necessitated by the occurrence of an AE(s) and/or study procedure(s).

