11. APPENDICES

Appendix 1: Adverse Event Reporting

Adverse Events

Definition of Adverse Events

An adverse event (AE; or adverse experience) is defined as any untoward medical occurrence experienced by a patient or healthy subject, whether or not considered drug related by the Investigator (or designee). A treatment-emergent AE is an AE that is reported after a dose of study drug.

The following are all AEs:

- Unfavorable changes in general condition;
- Subjective or objective signs/symptoms;
- Concomitant diseases or accidents;
- Clinically relevant adverse changes in laboratory parameters observed in a subject during a clinical study.

Adverse events comprise all disturbances of general health status, subjective and objective disease symptoms (including laboratory abnormalities that are deemed clinically significant by the Investigator or designee), and accidents observed in the context of a clinical trial, irrespective of a possible causal relationship with the administration of the trial substance.

Categorization of Adverse Events

The severity of AEs will be categorized based on the National Cancer Institute Common Terminology Criteria for Adverse Events (CTCAE) Version 5.0 as follows:

- **Grade 1 Mild:** Asymptomatic or mild symptoms; clinical or diagnostic observations only; intervention not indicated
- **Grade 2 Moderate:** Minimal, local or noninvasive intervention indicated; limiting age-appropriate instrumental Activities of Daily Living (ADL)*
- **Grade 3 Severe or medically significant but not immediately life threatening:** Hospitalization or prolongation of hospitalization indicated; disabling; limiting self-care ADL**
- **Grade 4 Life-threatening consequences:** Urgent intervention indicated
- **Grade 5 Death related to AE**

Note: Not all grades are appropriate for all AEs. Therefore, some AEs are listed within the CTCAE with fewer than 5 options for grade selection. Grade 5 (death) is not appropriate for some AEs and therefore is not an option.

* Instrumental ADL refer to preparing meals, shopping for groceries or clothes, using the telephone, managing money, etc.

**Self-care ADL refer to bathing, dressing and undressing, feeding self, using the toilet, taking medications, and not bedridden.

The Investigator (or designee) will make a determination of the relationship of the AE to the study drug using a 2-category system according to the following guidelines:

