- **NOT RELATED** = The time course between the administration of investigational product and the occurrence or worsening of the AE rules out a causal relationship and another cause (eg, concomitant drugs, therapies, complications, comorbidities) is suspected;
- **RELATED** = The time course between administration of investigational product and the occurrence or worsening of the AE is consistent with a causal relationship and no other cause (eg, concomitant drugs, therapies, complications, comorbidities) can be identified.

An AE is associated with the use of the drug if there is a reasonable possibility that the experience may have been caused by the drug.

Pregnancy

As information is available, a pregnancy (including pregnancy in female partners of male subjects) diagnosed through EOS or ET (if the subject discontinues from the study and does not complete a follow-up phone call) and for up to 90 days after study drug administration should be reported by the Investigator (or designee) via eFax to the Sponsor's clinical safety representative within 24 hours of being notified. The Sponsor's safety representative will then forward the Pregnancy Form to the Investigator for completion.

eFax: [contact]

A subject becoming pregnant while on study drug will immediately be withdrawn from the study and early termination study procedures will be performed. The subject or partner should be followed by the Investigator until completion of the pregnancy. If the pregnancy ends for any reason before the anticipated date, the Investigator should notify the Sponsor's clinical safety representative. At the completion of the pregnancy, the Investigator will document the outcome of the pregnancy. If the outcome of the pregnancy meets the criteria for immediate classification as a serious AE (SAE; ie, postpartum complication, spontaneous abortion, stillbirth, neonatal death, or congenital anomaly), the Investigator should follow the procedures for reporting an SAE.

Male subjects will be instructed to notify the Investigator immediately if they discover their sexual partner is pregnant. In this instance, the partner must provide written consent before pregnancy information can be collected. When a CRU becomes aware that the female partner of a male subject is pregnant, they are to contact the Investigator immediately (within 24 hours of the CRU staff becoming aware of the event) in addition to notifying the Sponsor's safety representative via eFax.

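### Appendix 1's two causality categories leave out an adverse event with plausible timing and another identified cause, and RELATED is stricter than the protocol's own reasonable-possibility test (low severity)

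*Protocol*

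**What the plan says.** Protocol Appendix 1 has the investigator make a "determination of the relationship of the AE to the study drug using a 2-category system according to the following guidelines". For NOT RELATED, the time course "rules out a causal relationship and another cause (eg, concomitant drugs, therapies, complications, comorbidities) is suspected". For RELATED, it "is consistent with a causal relationship and no other cause (eg, concomitant drugs, therapies, complications, comorbidities) can be identified". The next sentence adds a third formulation: "An AE is associated with the use of the drug if there is a reasonable possibility" of drug causation. The Reporting part of the same appendix then requires four things of an FDA-reportable event: it must be associated with the drug, serious, related and unexpected.

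The call is used in two other places that matter here. Under Protocol 7.2.1, non-serious events arising between end of treatment (EOT) or early termination (ET) and end of study (EOS) are reported only if judged related. Under SAP 10.4.1, the TEAE tables are produced twice, once for all causalities and once for related events, using the site investigator's assessment.

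The reference drug is named in two ways. The category definitions refer to the investigational product, while the sentence introducing them refers to study drug. The title page gives "Investigational Product: LOXO-292", and exclusion criterion 28 in Protocol 4.4 uses the term in that sense: "Have previously completed or withdrawn from any other study investigating LOXO-292, and have previously received the investigational product". The Synopsis heading "Investigational products, dose, and mode of administration" covers LOXO-292, ranitidine and omeprazole. Section 5.2 also treats all three as study drugs: "All study drugs will be administered orally with approximately 240 mL of water".

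**The concern.** With only two categories and no unassessable option, the definitions should cover every event between them. Here each is a conjunction, and neither is the negation of the other. The uncovered case is an ordinary one: an event that starts at a plausible time after LOXO-292 and for which the investigator can also point to something else.

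The design makes that case realistic. LOXO-292 is given on Day 12 within ranitidine dosing (Days 8 to 18) and on Day 23 within omeprazole dosing (Days 19 to 29), and concomitant drugs head the list of alternative causes in both definitions.

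An investigator must still choose, so two assessors could label the same event differently while both follow the text. What is at stake is the meaning of the related-TEAE tables, whether a late non-serious event is reported at all, and the site's view of whether a serious, unexpected event is FDA-reportable.

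**Working it through.** The plan gives no figure to reproduce, so the check is to apply the definitions to each combination of timing and other cause. Timing is taken as either consistent with causation or ruling it out. Suspected and identified are kept apart because the definitions use different verbs.

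| Timing | Other cause | RELATED met? | NOT RELATED met? |
|---|---|---|---|
| Consistent | None | Yes | No |
| Consistent | Suspected, not identified | Yes | No |
| Consistent | Identified | **No** | **No** |
| Ruled out | None suspected | **No** | **No** |
| Ruled out | Suspected or identified | No | Yes |

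Two rows meet neither definition.

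1. *Timing ruled out, no other cause suspected.* This is a gap on paper only. If timing excludes causation there is no reasonable possibility either, so every standard in Appendix 1 points to NOT RELATED.
2. *Timing consistent, other cause identified.* This gap has weight. Striking out RELATED because a cause is identified leaves NOT RELATED. Striking out NOT RELATED because timing does not exclude causation leaves RELATED. The reasonable-possibility sentence may favour RELATED, but it is not written as part of either category.

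Second check: the two standards side by side. An event counts as associated on a reasonable possibility, with no need to exclude other causes. It counts as related only if no other cause can be identified. An event in row 3 can therefore be associated and not related. The FDA-reportable definition requires both, so the stricter wording governs, and such an event can drop out at the site even though it passes the reasonable-possibility test.

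Third check: what depends on the call.

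- *Related-TEAE tables (SAP 10.4.1):* affected directly.
- *Non-serious events from EOT or ET to EOS (Protocol 7.2.1):* affected. The follow-up call is at 7 ± 2 days, so the window is 7 − 2 = 5 to 7 + 2 = 9 days; for completers, with EOT on Day 30, it ends between Day 35 and Day 39. An event judged not related in this window need not be reported, so the all-causality tables cannot recover it.
- *From Day 1 dosing to EOT or ET:* events are reported whatever their relationship, so the all-causality tables are intact.
- *SAEs:* notified to the sponsor within 24 hours whether related or not, and the final SUSAR determination is the sponsor's (Appendix 1).
- *PK endpoints:* not touched.

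**The case against.** The strongest reply is that Appendix 1 calls the definitions guidelines for a judgement the investigator makes, and that the reasonable-possibility sentence directly after them can be read as settling mixed-cause events. That reading is available, but the text does not state it, and the FDA-reportable definition treats associated and related as separate conditions. The Study Manual, which Appendix 1 says holds further reporting instructions, was not among the documents reviewed and may help.

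A second reply is that any wording leaves room for judgement. That stands: a reasonable-possibility test makes the categories exhaustive, not perfectly reproducible.

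A reader might also infer more than the documents support:

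- *That the protocol gives two contradictory definitions of related.* It does not. Associated is a different term; the mismatch is between two standards applied to the same reportability decision.
- *That related rows for the ranitidine-only and omeprazole-only labels in SAP 7 are judged against a LOXO-292 dose at least 7 days old (Day 8 − Day 1; Day 19 − Day 12).* This holds only if investigational product means LOXO-292 alone. The Synopsis heading supports the wider meaning, and the determination itself is to study drug, which Section 5.2 uses for all three. Under the wider meaning ranitidine and omeprazole would also no longer count as other causes, although comorbidities, complications and other therapies still would.
- *That the Safety Population wording shows a practical problem.* Protocol 8.2.1 refers to study drug and SAP 9 to LOXO-292, but LOXO-292 is the first drug given, so membership is the same.
- *That follow-up of ongoing events is lost.* Protocol 4.6 and 7.2.1 only permit extended follow-up of related events, and 7.2.1 follows subjects to EOS regardless of relatedness, with stated exceptions.
- *That the share of uncovered rows measures the effect.* It shows a gap in the logic and predicts no number of events.

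**Conclusion.** The point holds in limited form. As written, the two categories do not cover an event with consistent timing and another identified cause, and RELATED is stricter than the reasonable-possibility standard with which it is combined for FDA reportability. Confidence in this is high, because it follows from the wording alone.

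The consequences are small: a descriptive split of TEAEs, non-serious events in a 5-to-9-day window, and the site's FDA-reportable call, which is backed up by 24-hour SAE notification and the sponsor's own determination. Safety is a secondary objective in about 20 healthy subjects, and SAP 10.4.7 plans no inferential analysis. The number of events that would be labelled differently cannot be estimated from the documents. The conclusion assumes that the Study Manual adds no rule for mixed-cause events. Severity is low.

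**What to change.** Reconcile the category definitions, the sentence that follows them and the FDA-reportable definition in Appendix 1, so that the categories are exhaustive and rest on one standard. For example:

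- RELATED: there is a reasonable possibility that the study drug caused the AE; other possible causes do not preclude this.
- NOT RELATED: there is no reasonable possibility that the study drug caused the AE.

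As a minor consistency edit, use study drug in place of investigational product in these definitions, state which drug or drugs it covers for this assessment, and carry the same meaning into SAP 10.4.1.

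Changing *and* to *or* in NOT RELATED would also close the gap, but less well. An event with consistent timing and a suspected but unidentified cause would then fit both categories, and mixed-cause events would go to NOT RELATED even where a reasonable possibility remains.

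The cost is a rewording in Appendix 1 and one clarifying sentence in the SAP, with no new assessments or tables. Under Protocol 9.1 the change needs agreement between sponsor and investigator, and IRB approval if it is held to affect subject safety. The downside is that more events may be classed as related.

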4.3. Inclusion Criteria

Subjects who meet the following criteria at Screening and Check-in (Day -1), unless otherwise specified, may be included in the study:

1. Males, and females of nonchildbearing potential, between 18 and 55 years of age, inclusive, at Screening
2. Within BMI range 18.5 to 32.0 kg/m², inclusive
3. In good health, determined by no clinically significant findings from medical history, PE, 12-lead ECG, vital signs measurements, or clinical laboratory evaluations ([Appendix 4](#)) at Screening or Check-in as assessed by the Investigator (or designee)
4. Females of nonchildbearing potential, defined as being permanently sterile (ie, due to hysterectomy, bilateral salpingectomy, bilateral oophorectomy, or confirmed tubal occlusion more than 6 months prior to study drug administration) or postmenopausal (defined as at least 12 months postcessation of menses without an alternative medical cause). Postmenopausal status will be confirmed with a screening serum FSH level ≥ 40 mIU/mL. All females must have a negative qualitative serum pregnancy test (serum human chorionic gonadotropin) at Screening and Check-in (Day -1)

5. Males who are capable of fathering a child must agree to use one of the following methods of contraception from the time of the dose administration through 6 months after the last dose of LOXO-292 administration:

- Male sterilization, with documented confirmation of surgical success. Male subjects will be surgically sterile for at least 90 days prior to Check-in (Day -1). If documentation is not available, male subjects must follow one of the contraception methods below:
 - Male condom with spermicide, and
 - For a female partner of male study participant:
 - Intrauterine device (IUD) (hormonal IUD; eg, Mirena®). Copper IUDs are acceptable (eg, ParaGard®);
 - Established use of oral, implanted, transdermal, intravaginal, or hormonal method of contraception associated with inhibition of ovulation; or
 - Bilateral tubal ligation.

Males who practice true abstinence because of a lifestyle choice (ie, do not become abstinent just for the purpose of study participation) are exempt from contraceptive requirements. Periodic abstinence by a female partner (eg, calendar, ovulation, symptothermal, postovulation methods) and withdrawal are not acceptable methods of contraception. If a male subject is abstinent at the time of signing the ICF but becomes sexually active through EOS, he must agree to use contraception as described above.

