
For male subjects, sexual intercourse with female partners who are pregnant, or breastfeeding should be avoided. Male subjects are required to refrain from donation of sperm from Check-in (Day -1) until 6 months after administration of study drug.

For subjects who are exclusively in same-sex relationships, contraceptive requirements do not apply.

6. Able to understand and provide written informed consent
7. Able to comply with all study procedures, including the 30-night stay at the CRU and follow-up phone call

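### Two stated end dates fall short of the 6-month male contraception period: the abstinent-male clause stops at EOS, and the dated pregnancy-reporting sentence stops at 90 days

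*Protocol*

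**What the plan says.** **Contraception.** Protocol Section 4.3, inclusion criterion 5, asks men capable of fathering a child to use contraception "from the time of the dose administration through 6 months after the last dose of LOXO-292 administration".

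**Abstinent men.** The same criterion exempts "Males who practice true abstinence because of a lifestyle choice". It then adds that if a man who is abstinent at consent "becomes sexually active through EOS, he must agree to use contraception as described above". Appendix 4 (footnotes) defines EOS as the follow-up call 7 days (± 2 days) after EOT or ET.

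**Sperm donation.** Criterion 5 also has men "refrain from donation of sperm from Check-in (Day -1) until 6 months after administration of study drug".

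**Pregnancy reporting.** Appendix 1, under Pregnancy, has the Investigator report to the Sponsor within 24 hours any pregnancy ("including pregnancy in female partners of male subjects) diagnosed through EOS or ET") "and for up to 90 days after study drug administration". The sentence does not say which study drug, or which dose, starts the 90 days.

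**Undated duties in the same place.** "Male subjects will be instructed to notify the Investigator immediately if they discover their sexual partner is pregnant". "When a CRU becomes aware that the female partner of a male subject is pregnant, they are to contact the Investigator immediately", and they must also eFax the Sponsor's safety representative. All pregnancies go on the AE eCRF. None of these three sentences has an end date.

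Neither Letter of Administrative Change alters these texts. Letter No. 2 changes an inclusion criterion, but only the definition of female sterility.

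**The concern.** The sponsor has set 6 months after the last LOXO-292 dose as its own precautionary period, for a drug that Protocol Section 1.2 describes as embryo-lethal and toxic to development. One would expect the clauses that support that period to last at least as long, and two do not.

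- The abstinence clause names EOS as the last point at which a change in sexual activity triggers the duty. A man who becomes active after EOS, but within the 6 months, is not expressly covered.
- The 90-day sentence is the only one in the pregnancy text with a time limit. Site staff could take it as the end of reporting while men are still under the contraception rule.

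The EOS call is the last scheduled contact, and SAE collection ends there (Section 7.2.1). After that, capture of partner pregnancies rests on Appendix 1, so its one dated limit should be clear. Female subjects must be of nonchildbearing potential, so the point concerns partners of male subjects. It has no bearing on the PK endpoints or their analysis.

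**Working it through.** The check is study-day arithmetic; the plan gives no figure of its own to reproduce.

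**Inputs.** Last LOXO-292 dose Day 23, last omeprazole dose Day 29 and EOT Day 30 (Synopsis; Section 3.1). EOS is 7 ± 2 days after EOT (Appendix 4). Assumption: 6 calendar months is 181 to 184 days, depending on the calendar date.

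**End of contraception, completers.** 23 + 181 = Day 204; 23 + 184 = Day 207.

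**Abstinence clause.**
- EOS: 30 + 7 − 2 = Day 35 to 30 + 7 + 2 = Day 39.
- Shortfall: 204 − 39 = 165 days to 207 − 35 = 172 days.
- Subjects are confined until Day 30, so the clause covers only 35 − 30 = 5 to 39 − 30 = 9 days after discharge.

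**90-day reporting sentence.** The tables in Section 5.1 list LOXO-292, ranitidine and omeprazole all as study drugs, so both starting points are possible.

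| 90 days counted from | Ends | Shortfall |
|---|---|---|
| LOXO-292, Day 23 | 23 + 90 = Day 113 | 204 − 113 = 91 to 207 − 113 = 94 days |
| Omeprazole, Day 29 | 29 + 90 = Day 119 | 204 − 119 = 85 to 207 − 119 = 88 days |

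For completers the range is 85 to 94 days.

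**Early terminators.** Counted from their last LOXO-292 dose, the shortfall is 181 − 90 = 91 to 184 − 90 = 94 days. The last acid reducer can fall up to 10 days after that dose (Day 1 to Day 11, or Day 12 to Day 22). Counted from there, the shortfall can be as small as 181 − 100 = 81 to 184 − 100 = 84 days.

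Both end dates are therefore short on every reading of study drug and of month length. The reporting figures measure the dated sentence only. That sentence runs on date of diagnosis, whereas contraception concerns conception. Because diagnosis follows conception, a limit on diagnosis would have to run longer than the contraception period, not shorter, to cover the same pregnancies. A conception inside the 90 days but diagnosed afterwards already falls outside the sentence.

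**The case against.** **On reporting.** A reader might infer that partner pregnancies diagnosed after Day 113 or 119 go unreported. The documents do not support that. Appendix 1 has separate, undated sentences for exactly this group: the man tells the Investigator, and the CRU contacts the Investigator and eFaxes the Sponsor's safety representative, the same recipient and channel as in the dated sentence. The eCRF rule covers all pregnancies. The dated sentence says what should be reported; it does not say that later reports stop. This stands, and it reduces the point to a conflict between one dated sentence and several undated ones.

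**On abstinence.** A reader might infer that a man abstinent at consent is released from contraception after EOS. That goes too far. The exemption is for men who practise abstinence, so a man who becomes active no longer fits it and the main 6-month rule can be read to bind him. If he becomes active before EOS, the reference back to the methods above can be read as importing the full 6 months. What remains is the man who becomes active after EOS and reads the specific clause as limiting the general rule. With 20 subjects planned and at least 3 of each sex sought, that is one subset of about 17 men at most (20 − 3), before replacements.

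**On matching periods.** Nothing in the documents requires the reporting and contraception periods to be equal. That is so, but no reason is given for the shorter one.

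**On unseen material.** The consent pages were removed from the review copy, and Appendix 1 points to a Study Manual for further reporting instructions. Either may already instruct men for the full 6 months. This stands as a limit on confidence.

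**Conclusion.** The point holds as a minor misalignment and a cheap improvement. For completers, the abstinence clause ends 165 to 172 days before the contraception period, and the dated reporting sentence ends 85 to 94 days before it. The first leaves one narrow case without express cover. The second conflicts with undated duties that may still capture later pregnancies, so the protocol gives staff two answers. It is not a complete reporting gap, and it does not show that any man is released from contraception early. The figures rest on 6 months being 181 to 184 days and on study drug meaning either LOXO-292 or omeprazole. Confidence is medium, because the consent text and Study Manual were not available.

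**What to change.** - **Section 4.3, criterion 5:** in the clause for men abstinent at consent, replace EOS with 6 months after the last dose of LOXO-292.
- **Appendix 1, Pregnancy:** replace the 90-day limit with any pregnancy conceived up to 6 months after the last dose of LOXO-292, whenever diagnosed. Keep the man's, the CRU's and the eCRF duties without an end date.
- **Sperm donation:** leave unchanged. Its 6 months run from an unspecified study drug. If that includes omeprazole, tying the rule to LOXO-292 would shorten the ban by 29 − 23 = 6 days for completers, and by up to 10 days for early terminators.

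**Cost.** No visit or procedure is added. The site and Sponsor carry a longer passive reporting period: at least 85 to 94 more days for completers, then open-ended for late diagnoses of conceptions within the period. A change that affects subject safety needs written approval from the Sponsor, the Investigator and the IRB (Section 9.1), and the consent form may need matching words.
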